### 5.2.2 Thrombocytopenia:

If on the day of scheduled treatment with cisplatin the platelet count is < 75,000/mm^3, hold the second chemotherapy treatment but not the radiation until platelets are  $\geq$  75,000/mm^3, then treat at 100% dose.

### 5.2.3 Renal Adverse Events:

Cisplatin dose should be based on the serum creatinine or creatinine clearance immediately prior to the second cisplatin dose using the following guidelines:

Note: If creatinine is > 1.5 mg/dl, creatinine clearance must be calculated (Cockcroft-Gault) in order to make dose adjustment. The cisplatin dose will be determined as follows:

#### Serum Creatinine Clearance Cisplatin Dose

- $\leq$  1.5 mg/dl or > 50 ml/min full dose
- 1.5 mg/dl and < 50 ml/min Hold drug\*

\*Cisplatin should be held (but the RT continued) and the creatinine measured weekly, until it is

- < 1.5 mg/dl or the creatinine clearance is > 50 ml/min, and then the second dose of cisplatin can be given at the reduced dose by 50%.

### 5.2.4. Nausea and Vomiting:

Maximum supportive therapy will be given, and cisplatin will be continued at full dose for  $\leq$  grade 2 nausea and vomiting.

For grade 3 nausea and vomiting refractory to supportive therapy, cisplatin will be held until recovery to  $<$  grade 2. No dose reductions will be made.

### 5.2.4 Mucositis:

Significant mucositis (grade 3-4, NCI CTCAE, version 45.0) is expected from radiation and cisplatin and should not be a reason for a treatment break, unless it significantly interferes with fluid intake or nutrition. Aggressive supportive care is encouraged.

If a participant experiences several adverse events and there are conflicting recommendations, the investigator should use the recommended dose adjustment that reduces the dose to the lowest level.

### 5.2.5 Switching to weekly cisplatin from every-3-week cisplatin

If a participant experiences any of the above adverse events requiring dose modification, every-3-week cisplatin can be switched to weekly cisplatin at least 3 weeks after the first dose of every-3-week cisplatin, at the treating physician's discretion. All adverse events should be resolved to baseline or CTCAE grade  $\leq 1$  before weekly cisplatin can be resumed. If the switching happens, the participant can continue STS infusion at 10mg/m^2 as outline in section 5.1.

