Secondary Objectives	Secondary objectives are to 1) determine the rate of grade $\geq 2$ change of hearing impairment from baseline based on NCI CTCAE version 5.0 with use of STS after concurrent chemoradiation with cisplatin 3 months post-treatment, 2) determine the rate of tinnitus measured by PRO-CTCAE with use of STS 3 months post-treatment, 3) describe patient reported outcomes with STS measured with PRO-CTCAE for selected oral, GI, neurologic and perceptual symptoms 4) describe patient reported outcomes measured with Hearing Handicap Inventory for Adults – Screening (HHIA-S) compared to results from standard NRG Oncology head and neck trials (such as RTOG 1016).
Sample Size	A total of 16 patients are going to be enrolled.

Duration of Study Treatment	Participants may continue study treatment for up to 7 weekly doses or 3 every 21-day doses from the time of initiating treatment.
Duration of Follow up	Participants will be followed up to 3 months post-therapy from the completion of radiation.
Unique Aspects of this Study	This is the first study to evaluate the feasibility of STS in patients with locally advanced head and neck cancer undergoing concurrent chemoradiation therapy with cisplatin.

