### 3.2 Sample Size

Target accrual is a total of 16 patients, and to account for screen failures and withdrawals, we will consent up to 18 patients. Patients can be enrolled to the and can get concurrent chemoradiation with weekly cisplatin (40 mg/m^2) given once a week or concurrent chemoradiation with high dose cisplatin (80-100 mg/m^2) given every 3 weeks. Participants who do not receive any dose of STS will not be evaluable and will be replaced.

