**Table 5.1      Regimen Description**

Investigational Product	Premedication; precautions	Dose	Route	Schedule	Cycle Length
Cisplatin (weekly)	
 
Cisplatin can be given within 24 hours of radiation therapy. If radiation is held for more than 2 days (for any reason), cisplatin may be held as well until radiation resumes.
 
Prophylactic anti-emetic regimen will be given as per UCSF guidelines.
 
1 liter of isotonic fluid will be given intravenously prior to cisplatin infusion
 
	40 mg/m 	Intravenously	Days 1, 8, 15, 22, 29, 36, and 43	
Cisplatin (every-3-weeks)	
 
Cisplatin can be given within 24 hours of radiation therapy. If radiation is held for more than 2 days (for any reason), cisplatin may be held as well until radiation resumes.
 
Prophylactic anti-emetic regimen will be given as per UCSF guidelines.
 
1 liter of isotonic fluid will be given intravenously prior to cisplatin infusion
 
	80-100 mg/m 	Intravenously	Days 1, 22, and 43	Weekly or every 3 weeks
*Sodium Thiosulfate (weekly)	No contraindications	10 g/m 	Intravenously using a Mediport or a PICC line	Between 4-5 hours after each cisplatin infusion sodium thiosulfate will be	

				administered over 1-2 hours	
*Sodium Thiosulfate (every-3-week)	No contraindications	20 g/m 	Intravenously using a Mediport or a PICC line	Between 4-5 hours after each cisplatin infusion sodium thiosulfate will be administered over 1-2 hours	

\*Missed doses of sodium thiosulfate will not be replaced.

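### Section 5.2.5 times the switch to weekly cisplatin from the first high dose only, so its literal wording allows a more concentrated course than either regimen in Table 5.1

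*Combined protocol and SAP*

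**What the plan says.** Section 5.2.5 opens the switch with "If a participant experiences any of the above adverse events requiring dose modification" and then sets the timing: "every-3-week cisplatin can be switched to weekly cisplatin at least 3 weeks after the first dose of every-3-week cisplatin". It adds a recovery condition, "All adverse events should be resolved to baseline or CTCAE grade" 1 or lower, and leaves the decision to the treating physician. It gives no interval from any later high dose, no number of weekly doses after the switch and no combined limit.

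Table 5.1 lists two unmixed schedules. High-dose cisplatin, 80 to 100 mg/m², is given on "Days 1, 22, and 43". Weekly cisplatin, 40 mg/m², is given on "Days 1, 8, 15, 22, 29, 36, and 43". The Abstract limits treatment to "up to 7 weekly doses or 3 every 21-day doses". The Section 6.1 calendar lets the physician omit Day 43, and Section 3.5 sets a treatment duration of 7 weeks.

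Sections 5.2.1 to 5.2.3 (blood counts and renal function) word their holds around the second cisplatin treatment. The nausea and vomiting rule and the mucositis rule that follow are not tied to a particular dose.

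**The concern.** A minimum gap before weekly dosing protects the patient only if it runs from the dose that precedes the switch. Here it runs from the first high dose, so it is used up by Day 22 whatever is given that day. From then on the rule imposes no wait, although Table 5.1 and the Abstract space high doses 21 days apart.

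The patients concerned have just had toxicity that called for dose modification. The literal text lets them receive cisplatin at a greater intensity than either planned regimen, so the issue is chiefly one of participant safety and clarity. It also bears on interpretation: Section 1.1 describes ototoxicity as dose-dependent, and Section 2.3 reports hearing by cohort, yet a mixed course matches neither schedule.

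**Working it through.** **The plan's own figure.** Section 5.4 gives a target cumulative dose of 200 mg/m², described as similar for the two regimens. Five weekly doses give 5 × 40 = 200 and two high doses give 2 × 100 = 200, so the figure reproduces. At the permitted 80 mg/m², 2 × 80 = 160, which falls short. The documents state no maximum cumulative dose; the maxima below are dose times number of doses.

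**Inputs.** High dose d = 80 to 100 mg/m² on Days 1, 22 and 43; weekly dose 40 mg/m², with Days 29, 36 and 43 available (Table 5.1). Nominal days are used throughout.

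**Does the text permit the path?**
- Day 22 − Day 1 = 21 days, so the timing condition is met from Day 22.
- Day 29 − Day 1 = 28 days, which satisfies it; Day 29 − Day 22 = 7 days, which it does not address.
- Two high and three weekly doses lie within the Abstract's counts of 3 and 7.
- Day 43 lies within 7 weeks.
- Recovery and physician judgement set no interval.

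**Dose on the path** (mg/m²).
- Total: d + d + 3 × 40 = 2d + 120.
- Largest amount in 21 days (Day 22 to Day 42): d + 2 × 40 = d + 80.
- Table 5.1 totals: 3d every 3 weeks, at most 3 × 100 = 300; weekly 7 × 40 = 280.
- Table 5.1 amounts in 21 days: d every 3 weeks; weekly 3 × 40 = 120.

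| d | Own total, 3d | Switched total, 2d + 120 | Against 280 | Against 300 | Switched, 21 days | Every 3 weeks, 21 days | Weekly, 21 days |
|---|---|---|---|---|---|---|---|
| 80 | 240 | 280 | equal | below | 160 | 80 | 120 |
| 90 | 270 | 300 | above | equal | 170 | 90 | 120 |
| 95 | 285 | 310 | above | above | 175 | 95 | 120 |
| 100 | 300 | 320 | above | above | 180 | 100 | 120 |

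The switched total exceeds 3d whenever d < 120, so across the whole permitted range. It exceeds 280 when d > 80 and 300 when d > 90.

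**What changes these results.**
- *Day 43 omitted:* the total is 2d + 80 = 240 to 280, never above 280 or 300, and no longer above 3d. The 21-day figure is unchanged, because it uses Days 22, 29 and 36 only.
- *Second dose halved under the renal rule:* the total is at most d + d/2 + 120 = 240 to 270, below both maxima. The 21-day figure falls to d/2 + 80 = 120 to 130.
- *STS, using Table 5.1 doses:* 20 + 20 + 3 × 10 = 70 g/m², equal to 7 × 10 = 70 on the weekly schedule. The excess over the table concerns cisplatin.

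**The case against.** The strongest reply is that the authors meant a switch in place of the second high dose. The preceding rules on blood counts and renal function speak of the second treatment. On that reading the first dose is also the most recent one, and the gap is 21 days. The total would be d + 4 × 40 = 240 to 260 mg/m², with at most 120 in 21 days, so neither maximum is exceeded. This is a plausible account of intent. But Section 5.2.5 does not state it, and its trigger also takes in rules not limited to the second dose, such as that for grade 3 nausea and vomiting.

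The path is also narrow. Blood-count holds apply on a scheduled treatment day, and after Day 22 the next one for this group is Day 43. All adverse events must have settled to baseline or grade 1 or lower, in a setting where the mucositis rule expects grade 3 to 4 events. The physician must also choose to switch. These points make the path uncommon; they do not close it.

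A switch rule is by nature an exception to the regimen table, so this is not a flat contradiction. That is fair, but an exception still needs to say which of the table's limits continue to apply.

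A reader might infer that the path adds failures on the primary endpoint. The documents do not support this. Such a patient has already had the two high doses that Section 2.2 requires; only a later treatment-related delay of more than 7 days could count, and the text does not say how delay is judged after a switch. Nor does it add failures under the Section 5.4 rule: at 100 mg/m² the 200 mg/m² threshold is already met, and at 80 mg/m² one weekly dose takes 160 to 200.

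**Conclusion.** The point holds as a gap in a stated safeguard. With a full second high dose on Day 22 and weekly doses on Days 29 and 36, the literal text allows 160 to 180 mg/m² in 21 days, above both Table 5.1 regimens at every permitted high dose. This is the robust result.

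The cumulative result is conditional. With all three weekly doses the total is 280 to 320 mg/m², always above that patient's own three-dose total of 240 to 300. It exceeds both 300 and 280 only when the high dose is above 90 mg/m² and Day 43 is given. A reader might conclude that every exposure in the table is exceeded; at 80 mg/m² the total only equals the weekly maximum and is below 300, so that goes too far.

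The conclusion rests on the literal wording, nominal days and maxima derived by multiplication. The documents give no switching frequency, so no trial-level effect can be stated.

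**What to change.** Reconcile Section 5.2.5 with Table 5.1, the Abstract's dose limits and the second-dose wording of Sections 5.2.1 to 5.2.3. The amended text should state how the minimum interval and the dose limits apply to a switched, mixed course. The content is for the clinical team to decide; this review proposes no interval, dose or switch rule.

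The same paragraph gives the STS dose after a switch in mg/m², where Table 5.1 uses g/m². The two should be reconciled in the same amendment.

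The cost is one or two sentences, with no added patients, visits or tests. Depending on what is decided, there may be less flexibility for a patient who has toxicity after a second high dose.

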## Abstract

Title	A Phase II study of Sodium thiosulfate (STS) for prevention of ototoxicity in patients with locally advanced squamous cell carcinoma of head and neck (SCCHN) undergoing concurrent chemoradiation with cisplatin
Study Description	This is a phase II study to establish feasibility of using sodium thiosulfate after intravenous cisplatin in head and neck cancer patients undergoing definitive concurrent chemoradiation for prevention of ototoxicity. Hypothesis is that use of intravenous STS would be feasible and safe in patients with locally advanced SCCHN undergoing concurrent chemoradiation with cisplatin. This is a prospective clinical trial for patients getting either weekly cisplatin (40mg/m  ) or every-3-week cisplatin (100mg/m  ). A total of 16 patients will be enrolled and each subject will have baseline and post-treatment (3 months after the completion of concurrent chemoradiation) audiogram to assess hearing loss as defined by NCI CTCAE version 5.0. STS (10 g/m  for weekly cisplatin group and 20g/m  for high dose cisplatin group) will be infused 4 hours after each cisplatin infusion is completed. Feasibility will be assessed by successful completion of planned treatment, defined by completion of 5 weekly cisplatin or 2 high dose cisplatin without any extended treatment related delays more than > 7 days.
Phase of Study	Phase II Study
Investigational Products	Sodium thiosulfate (STS)
Study population	Patients with locally advanced SCCHN (oral cavity, oropharynx, hypopharynx, and larynx) eligible for definitive concurrent chemoradiation with cisplatin would be eligible for the study. Patients must be at least 18 years old at the time of enrollment. Women and persons from ethnic minority groups are encouraged to participate the study.
Primary Objective	Primary objective is to establish feasibility of intravenous STS after each dose of concurrent cisplatin in patients with locally advanced head and neck squamous cell carcinoma undergoing definitive radiotherapy.

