### 1.4 Rationale for the Dose Selection/Regimen

Intravenous STS 10 g/m^2 or 20 g/m^2 will be administered over 1-2 hours, 4 hours after each cisplatin dose is completed, depending on weekly or high dose cisplatin regimen. In recent clinical trials in pediatric cancer patients, STS 20 g/m^2 infused after 6 hours of cisplatin has been well tolerated with little compromise in oncologic outcome. STS can reduce toxicities from cisplatin by quenching reactive oxygen species, preserving the activity of antioxidant enzymes, and forming biologically inactive complexes with cisplatin to effectively reduce the systemic exposure to cisplatin. In pediatric hepatoblastoma study, STS 20 g/m^2 was given after cisplatin 80mg/m^2. For lower dose, weekly cisplatin, 10g/m^2 would be reasonable, as only half dose of cisplatin (40mg/m^2) is given. In animal studies, STS given 4 hours after cisplatin was able to protect rats from ototoxicity with minimal compromise in anti-tumor activity of cisplatin, whereas STS 8 and 12 hours after cisplatin had less and no protective effects at all [13]. STS is a FDA approved agent for treatment of cyanide poisoning and it is approved to be given as a single dose of 12.5g after infusion of 300mg of sodium nitrite. In a phase 3 trial for calciphylaxis, STS is given 25 g per day for 3 times a week[14].

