## 6.1 Study Calendar

### Weekly cisplatin

Period/Procedure	Screening	Cycle 1 and Future Cycles								End of Treatment	Long Term/Survival Follow 
Study Day/ Visit Day	-28	1 (+/- 2 days)	8 (+/- 2 days)	15 (+/- 2 days)	22 (+/- 2 days)	29 (+/- 2 days)	36 (+/- 2 days)	43*  (+/- 2 days)	133 (+/- 30 days)	Every 3 months (+/- 30 days)	
Study Treatment/Drug Administration											
Cisplatin		X	X	X	X	X	X	X			
Sodium Thiosulfate		X	X	X	X	X	X	X			
Clinical Assessments											
Physical exam	X	X	X	X	X	X	X	X	X		
Medical history	X										
Vital signs	X	X	X	X	X	X	X	X	X		
Concomitant medications	X	X	X	X	X	X	X	X	X		
AE assessment		X	X	X	X	X	X	X	X		

Long Term/Survival Follow-up will occur every 3 months via telephone calls up to 36 months.

 Day 43 can be omitted at the discretion of treating physician

Period/Procedure	Screening	Cycle 1 and Future Cycles								End of Treatment	Long Term/Survival Follow-Up 
Study Day/ Visit Day	-28	1 (+/- 2 days)	8 (+/- 2 days)	15 (+/- 2 days)	22 (+/- 2 days)	29 (+/- 2 days)	36 (+/- 2 days)	43*2 (+/- 2 days)	133 (+/- 30 days)	Every 3 months (+/- 30 days)	
Disease assessment 	x										
Performance status	x	x	x	x	x	x	x	x	x		
Audiogram	x								x		
Survival/Long-term Follow-up										x	
Questionnaires											
HHIA-S	x				x				x		
*PRO-CTCAE	x				x§ 				x		
Laboratory Assessments											
Hematology 	x	x	x	x	x	x	x	x	x		
Chemistry 	x	x	x	x	x	x	x	x	x		

 Documentation of disease assessment using AJCC Cancer Staging Manual 8th edition §PRO-CTCAE can be obtained between days 14 and 23 Including CBC with differential and platelet count Including alkaline phosphatase (ALP), aspartate aminotransferase/alanine aminotransferase (ALT/AST), total bilirubin, calcium, phosphorus, blood urea nitrogen (BUN), creatinine, total protein, albumin, glucose, potassium, sodium, chloride, bicarbonate

Period/Procedure	Screening	Cycle 1 and Future Cycles							End of Treatment	Long Term/Survival Follow-Up 

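### Section 5.2.5 gives the post-switch sodium thiosulfate dose in mg/m² where the section it cites gives g/m², a 1000-fold unit error in a dosing instruction

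*Combined protocol and SAP*

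**What the plan says.** Section 5.2.5 covers participants on every-3-week cisplatin who have an adverse event that requires dose modification. The treating physician may move them to weekly cisplatin, "at least 3 weeks after the first dose of every-3-week cisplatin", once the events have settled. On STS after the switch, the section says that "the participant can continue STS infusion at 10mg/m"² and adds "as outline in section 5.1".

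The weekly STS dose is stated in three other places, each time in grams:

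- Section 5.1, Table 5.1, weekly STS row: "Sodium Thiosulfate (weekly) No contraindications 10 g/m"²
- Section 1.4, dose rationale: "For lower dose, weekly cisplatin, 10g/m"²
- Abstract, Study Description: "STS (10 g/m 2 for weekly cisplatin group"

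Table 5.1 gives 20 g/m² STS with every-3-week cisplatin.

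**The concern.** The sentence names a dose and points to a section for its source, and the two differ in unit. It is also the only sentence that sets the STS dose for switched participants, so staff would consult it when a switch happens, and a dose-deviation check might be built on it.

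Taken literally, a switched participant would receive almost no STS for the rest of the course. That would bear on the descriptive secondary outcomes (hearing, tinnitus and the other patient-reported measures). It would also bear on the safety summaries, because Section 7.1.2 analyses everyone given at least one STS dose and Section 8 counts drug-related and serious events up to 7 days after the last one. Conversely, a participant correctly given 10 g/m² would appear to have had 1000 times the dose written in Section 5.2.5. With 16 participants planned, even one such case would be noticeable.

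**Working it through.** **Unit comparison.** Section 5.2.5: 10 mg/m². Table 5.1, weekly STS row: 10 g/m² = 10,000 mg/m². Ratio: 10,000 / 10 = 1000.

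**Which unit fits the design.** Section 1.4 sets the weekly STS dose at half of 20 g/m² because the weekly cisplatin dose, 40 mg/m², is half of the 80 mg/m² used in the paediatric trial. The STS-to-cisplatin mass ratios are:

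| Regimen | STS / cisplatin (mg/m²) | Ratio |
|---|---|---|
| Every 3 weeks, Table 5.1 | 20,000 / 100 to 20,000 / 80 | 200:1 to 250:1 |
| Weekly, Table 5.1 | 10,000 / 40 | 250:1 |
| Weekly after switch, Section 5.2.5 as written | 10 / 40 | 0.25:1 |

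Only grams fit. Nothing in the protocol supports an STS dose in mg/m².

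**Size per dose.** The documents give no body surface area, so 1.6–2.2 m² is assumed. Section 4.1.1 gives the solution strength as 250 mg/mL.

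- As written: 1.6–2.2 m² × 10 mg/m² = 16–22 mg; divided by 250 mg/mL, 0.064–0.088 mL.
- Table 5.1: 1.6–2.2 m² × 10 g/m² = 16–22 g; divided by 0.25 g/mL, 64–88 mL.

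**Size over the course.** The weekly schedule is "Days 1, 8, 15, 22, 29, 36, and 43", and the Section 6.1 calendar adds "Day 43 can be omitted at the discretion of treating physician". Assume no missed doses and a literal reading throughout. Each every-3-week dose contributes 20 g/m². Each post-switch dose contributes 10 g/m² as intended, or 0.01 g/m² as written.

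| Pattern | Intended (g/m²) | Literal (g/m²) | Received | Shortfall |
|---|---|---|---|---|
| One every-3-week dose, then weekly Days 22, 29, 36, 43 | 20 + 4×10 = 60 | 20 + 4×0.01 = 20.04 | 33.4% | 66.6% |
| One every-3-week dose, then three weekly doses (Days 22–36 with Day 43 omitted, or Days 29–43) | 20 + 3×10 = 50 | 20 + 3×0.01 = 20.03 | 40.1% | 59.9% |
| Two every-3-week doses, then weekly Days 29, 36, 43 | 40 + 3×10 = 70 | 40 + 3×0.01 = 40.03 | 57.2% | 42.8% |
| Two every-3-week doses, then weekly Day 43 only | 40 + 10 = 50 | 40 + 0.01 = 40.01 | 80.0% | 20.0% |

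**What is not touched.** The primary endpoint counts cisplatin administrations and treatment delays (Section 2.2). The stopping rule counts participants who do not reach 200 mg/m² cumulative cisplatin (Section 5.4). The sample size rests on a margin of error for a proportion (Section 8.2). None of these uses the STS amount.

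**The case against.** The best case against giving this weight is that the sentence largely corrects itself. It sends the reader to Section 5.1, where there is one weekly STS row and it says 10 g/m². Section 5.2.5 gives no reason for a different dose. A literal order would be under 0.1 mL of a drug supplied in 12.5 g vials and infused over 1–2 hours, for someone normally already given 20 g/m², and the investigational pharmacy would very likely query it.

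The course figures also depend on a switch occurring, on literal compliance and on no one correcting the dose. The 67% end needs weekly dosing to start on Day 22 itself. A participant whose toxicity is found on that day's tests would have cisplatin held until recovery and start later. Starting on Day 29 with three doses gives a shortfall of about 60%.

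All of this is fair on likelihood: actual misdosing is improbable, and the range describes a scenario and not an expected effect. It does not make the sentence right. A dosing instruction for the investigational product should not depend on the reader noticing that its unit is wrong.

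**Conclusion.** The concern holds. Section 5.2.5 is wrong by a factor of 1000 against the section it cites and against two further statements of the same dose. The error is almost certainly typographical, runs towards underdosing and affects only switched participants. Its consequence, if followed literally, is a loss of about 20–67% of course STS in such a participant. That range rests on no missed doses and uncorrected literal use; it does not depend on body surface area, which enters only the per-dose figures. The number of participants affected cannot be estimated because no switching rate is given. The design, primary endpoint, stopping rule and sample size are unaffected. It should be corrected because of where it stands, not because harm is likely.

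**What to change.** In Section 5.2.5 replace the milligram unit so that the post-switch STS dose reads 10 g/m². Alternatively, delete the figure and refer only to the weekly STS row of Table 5.1, which leaves a single source for the dose. Check that any order set or deviation check for switched participants uses grams. The protocol change is one line and alters nothing in the design, sample size or analysis.
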